### **6.2 Methods of minimising bias**

#### **6.2.1 Randomisation**

The randomization list will be created by the CTU-EOC and the randomization will be performed by the authorized personnel (physician responsible for the study, the anaesthetist and the surgeons) of the participating centre via RedCap®. Only the physician responsible for the study, the anaesthetist and the surgeons will be informed about the treatment arm.

#### **6.2.2 Blinding procedures**

The study is single blind: an expert from the anaesthesiology team will perform the nerve block, the surgeon will be informed about the group of randomization. The nursing personnel and patients that will fulfil the VAS scale formularies at 6, 12, 24, 48 hours are blinded, they will not know the arm of treatment.

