	
The pudendal nerve block with local anaesthetic is effective to reduce the postoperative pain for up to 24 hours. Currently no randomized study compares the effectiveness of perianal nerve blocks as adjuvant to spinal anaesthesia in the management of postoperative pain in patients undergoing hemorrhoidectomy. On the other hand, the pudendal nerve block procedure is safe, economic and simple. Complications related to the procedure such as intravenous injection of the anaesthetic, the formation of a retroperitoneal hematoma or abscess of the psoas muscle are described, although extremely rare.
 
The aim of this prospective randomized double-blind study is to compare the postoperative pain in patients undergoing Milligan Morgan hemorrhoidectomy under spinal anaesthesia with or without the pudendal nerve block.

Objective(s):	The objective is to assess the efficacy of the pudendal nerve block in patients treated by hemorrhoidectomy under spinal anaesthesia
Outcome(s):	
Primary outcome:
 
 
• Postoperative pain measured on VAS scale at 6, 12, 24, 48 hours
 
 
Secondary outcomes:
 
 
• Antalgic drugs as needed (opioids needed)
 
• Length of hospital stay
 
• Safety of the pudendal nerve block
 

Study design:	Randomized control single-blind trial
Inclusion / Exclusion criteria:	
Inclusion criteria:
 
 
• Patients affected by haemorrhoids (grade III and IV) and treated with Milligan-Morgan hemorrhoidectomy under spinal anaesthesia
 
• Signed informed consent
 
 
Exclusion criteria:
 
 
• Age < 18 year-old
 
• Pregnancy
 
• Allergy to local anaesthetics
 

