### **6.3 Unblinding Procedures (Code break)**

The Principal Investigator will be informed on the randomization and will be available 24/24 hours, 365 days/year in case of complications related to the pudendal nerve block occur. In case of serious complications also the authorized personnel (physician responsible for the study, the anaesthetist and the surgeons) will have the possibility to access to the randomization, the principal investigator will be always get informed.

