#### **8.1.2 Control Intervention**

In the postoperative period all the patients will receive metronidazole 500 mg x3 + paracetamol 1 gr x4 + NSAID + opioids as needed for at least 24 hours. Opioids used will be “strong opioids” (Pethidine 50 mg sc or Oxycodone Kaps 5 mg)

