
This procedure is usually a quite painful technique; thus, it is important to perform it after the spinal anaesthesia. It would be necessary to do it before the spinal anaesthesia just in case the pain would be associated to a nerve lesion. In this study the infiltration is not done on the nerve but in a muscular plane, thus is not needed the patient’s sensibility.

The procedure will be performed at our institution by one of the three expert anaesthesiologists in the peripheral nerves’ blockage. Those anaesthesiologists are:

- [name]. [name], Primario di Anestesia ORBV
- [name]. [name], Caposervizio Anestesia ORBV, board member of the Swiss Society of Loco-regional Anaesthesia
- [name]. [name], Caposervizio Anestesia e responsabile terapia del dolore ORBV

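### Surgeons are told the arm without need, and the spinal, the NSAID and discharge are not fixed before allocation is known; a cheap change would protect co-analgesia and length of stay

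*Combined protocol and SAP*

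**What the plan says.** **Who knows the arm.** Section 6.2.1 states: "Only the physician responsible for the study, the anaesthetist and the surgeons will be informed about the treatment arm". The synopsis (Measurements and procedures) and Sections 6.1 and 7.3 repeat this. All four places also name the surgeons among those who may perform the randomisation. Section 6.2.2 says again that the surgeon is told: "an expert from the anaesthesiology team will perform the nerve block, the surgeon will be informed about the group of randomization". Sections 6.3 and 10.1.1 give the Principal Investigator standing knowledge of the allocation. By Section 1.2 that person is also the sponsor, and the synopsis lists the sponsor as a senior surgeon.

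**Who does the block.** Section 8.2.1: "The procedure will be performed at our institution by one of the three expert anaesthesiologists".

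**Who is blinded.** Section 6.2.2: "The nursing personnel and patients that will fulfil the VAS scale formularies at 6, 12, 24, 48 hours are blinded".

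**What is fixed for all patients.** Section 8.1.2 gives "metronidazole 500 mg x3 + paracetamol 1 gr x4 + NSAID + opioids as needed for at least 24 hours" and names two rescue opioids. The synopsis gives the same background regimen for at least 48 hours. Section 8.5 bars other relevant concomitant treatment in general terms.

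**Outcomes affected.** The primary outcome is VAS pain (Section 5.1). Section 5.2 adds the type and number of as-needed analgesics, and length of stay in days.

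**Label.** The synopsis background says "The aim of this prospective randomized double-blind study is to compare the postoperative pain". The title, the design row and Sections 3.1, 6.1 and 6.2.2 say single-blind.

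**The concern.** Blinding the VAS raters protects the reading of pain. It does not protect the treatment received before the reading. If someone who knows that a patient has no block chooses a different spinal or a stronger NSAID order, the patient's pain really is lower, and a blinded nurse records it faithfully. Extra co-analgesia in Group B therefore shrinks the VAS difference. Length of stay is exposed more directly, because a discharge decision made with knowledge of the arm can create a difference where the block has no effect on stay.

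Knowledge of the arm is unavoidable for the anaesthetist who gives the block. For the surgeon it is avoidable, and the protocol gives nothing in return for it.

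**Working it through.** **1. Does the surgeon need the arm?** The surgeon does not perform the block (Section 8.2.1), and the operation is Milligan-Morgan haemorrhoidectomy in both groups (synopsis). No section gives a reason for disclosure.

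**2. What is left open once the arm is known?**

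| Element | Fixed in the text? | Known to be set by |
|---|---|---|
| Spinal | Named only; no agent, dose or additive | The anaesthetist, by implication; also told the arm |
| Metronidazole, paracetamol | Dose and frequency given | Not stated |
| NSAID | Class only | Not stated |
| Rescue opioid | Two options, no rule for choosing | Not stated |
| Discharge | No criterion in the text provided | Not stated |

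Section 8.1.1 places randomisation before the block. Nothing requires the spinal plan or the analgesic orders to be settled before the arm is seen.

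**3. The plan's own figure.** Section 11.2 gives 18 evaluable patients per group. With 10% drop-out, 18 / (1 − 0.10) = 20 per group, as stated. The 18 itself cannot be reproduced, because neither a baseline VAS nor an SD is given. At two-sided 5% and 80% power it implies a standardised effect of √(2/18) × (1.960 + 0.842) = 0.934 SD. (Section 6.1 mentions 100 patients; that conflict is a separate matter.)

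**4. Can the bias be sized?** The shift in mean VAS is the between-arm difference in the proportion given extra analgesia, multiplied by the effect of that analgesia. Neither factor is in the documents, so no estimate is possible. The table gives a scale only. The shift b is **assumed**, with n = 18 per group and a normal approximation, so the standard error of the difference is √(2/18) = 0.333 SD.

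- Power when b masks part of the effect: Φ((0.934 − b)/0.333 − 1.960)
- Two-sided error when b acts with no true effect: Φ(b/0.333 − 1.960) + Φ(−b/0.333 − 1.960)

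| Assumed b (SD) | Share of planned effect (b/0.934) | Power if masking | Error rate if no true effect |
|---|---|---|---|
| 0 | 0% | 80% | 5.0% |
| 0.1 | 11% | 71% | 6.0% |
| 0.2 | 21% | 60% | 9.2% |
| 0.3 | 32% | 48% | 14.7% |
| 0.5 | 54% | 26% | 32.3% |

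The power column concerns the VAS outcome, where compensation in Group B works against the block. The error column concerns an outcome such as length of stay, where knowledge of the arm could favour the block. For a skewed stay in days it is only a rough guide.

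**The case against.** Single-blind with blinded raters is a declared design, so blinding the surgeon improves the plan rather than repairs an error. That stands. It also stands that the primary-outcome bias described here is dilution, which cannot by itself produce a false claim of superiority.

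Four stronger readings are tempting, and the documents do not support them.

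- **That the surgeons control the NSAID and discharge.** No section says who does either. It is a likely inference only. As-needed opioid counts are partly protected if the blinded nurses give the doses.
- **That nothing prevents extra local anaesthetic at the wound.** Section 8.5 is a general bar on other treatment. It does not fix the spinal or define the permitted NSAID, so those two gaps remain.
- **That Section 6.3 shows the surgeons were meant to be blinded.** On access to the allocation it says "In case of serious complications also the authorized personnel (physician responsible for the study, the anaesthetist and the surgeons) will have the possibility to access", but the same sentence lists the anaesthetist, and the one giving the block cannot be blinded. The wording fits poorly with disclosure elsewhere, but it proves no intent. The single use of double-blind in the synopsis proves none either.
- **That discharge rules do not exist.** Section 17 lists an outpatient protocol whose content is not visible here. The absence is confirmed only for the text provided.

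Finally, any compensation through the spinal runs through the anaesthetist. Blinding surgeons does nothing for that route, so a second measure is needed.

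**Conclusion.** The point holds as a cheap improvement in freedom from bias. Three things are established from the text: the surgeons are told the arm and may randomise without a stated reason; the spinal and the NSAID are not specified; and nothing requires them to be set before allocation is seen. That bias follows is conditional on staff who know the arm setting these treatments or deciding discharge. Its size is unknown, and the table above is a scale under assumed shifts, not an estimate. A reader might infer that the primary result would be invalid or falsely positive. The documents do not support that: VAS raters are stated to be blinded, and the route described lowers the chance of showing a benefit. Length of stay is the outcome for which a spurious advantage is possible.

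**What to change.** 1. **Withhold the arm from the surgeons.** In the synopsis (Measurements and procedures) and Sections 6.1, 6.2.1, 6.2.2 and 7.3, remove the surgeons from those told the arm and, wherever they are listed, from those who randomise. The block anaesthetist randomises in REDCap. Amend Sections 6.3 and 10.1.1 so that a Principal Investigator who operates on or discharges participants learns the arm only through the Section 6.3 code break. Bring double-blind in the synopsis background into line with the rest.
2. **Record orders before the arm is shown.** Make REDCap require the spinal plan and the postoperative analgesic orders, including the NSAID, before it displays the arm. Take them from one order set common to both arms, with content chosen by the sponsor, and log later departures. This also covers the anaesthetist.
3. **Reconcile the related passages at the same time.** The synopsis places the block after the spinal. Section 6.1 places it before. Sections 3.3 and 8.2.1 open with before and then argue for after. The postoperative regimen lasts at least 48 hours in the synopsis and at least 24 in Section 8.1.2. The sponsor must settle both.

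I do not propose hiding the block from the ward chart: concealing a given local anaesthetic from treating staff is a safety trade-off that this gain does not justify.

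**Cost.** Amendment wording, a REDCap field order and a theatre routine, with no extra staff or patients and no change in sample size. The downside is that a surgeon who suspects a block complication must use the code break; Section 3.5 puts surgeons on the team that responds to such complications, so access must be prompt.

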Measurements and procedures:	
Patients' clinical data and operative time will be collected
 
Patients selected will be randomized in two groups.
 
 
• Group A will undergo Milligan-Morgan hemorrhoidectomy under pudendal nerve block plus spinal anaesthesia
 
• Group B will undergo Milligan-Morgan hemorrhoidectomy under spinal anaesthesia
 
 
The randomization list will be created by the CTU-EOC and the randomization will be performed by the authorized personnel (physician responsible for the study, the anaesthetist and the surgeons) of the participating centre via RedCap®. Only the physician responsible for the study, the anaesthetist and the surgeons will be informed about the treatment arm.

	
After the operation all the patient will receive Metronidazole 500 mg x3 + Paracetamol 1 gr x4 + NSAID + opioids as needed for at least 48 hours. The postoperative pain will be evaluated at 6, 12, 24, 48 hours with VAS scale both as in-patients or out-patients on specific formularies. In-patients will be then controlled after 1 months, while out-patients after 1 and 4 weeks.
 
Results will be collected on specific printed Case report form. The Principal Investigator will preserve the sensitive data in his office in a closed cabinet key. Results will be then collected on a Redcap® electronic database. The access to the database will require username and password. Only the authorized personnel (physicians responsible for the study) will have the access rights and all changes on the database are trackable.

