## **6. STUDY DESIGN**

### **6.1 General study design and justification of design**

This study is a randomized control single blind trial.

Patient will be randomized: Group A will undergo the pudendal nerve block under ultrasonographic control with injection of 10 mls of ropivacaine 0.75% before the spinal anaesthesia.

The population include patients with haemorrhoids (grade III and IV)

The study is single blind: an expert from the anaesthesiology team will perform the nerve block, the surgeon will be informed about the group of randomization. The nursing personnel (blinded) or the patient itself on specific formularies will evaluate the VAS scale at 6, 12, 24, 48 hours.

The comparator is no treatment

The method of randomization will be created by the CTU-EOC and the randomization will be performed by the authorized personnel (physician responsible for the study, the anaesthetist and the surgeons) of the participating centre via RedCap®. Only the physician responsible for the study, the anaesthetist and the surgeons will be informed about the treatment arm.

The expected duration of the study is 2 years, 100 patients.

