### **8.2 Administration of experimental and control interventions**

#### **8.2.1 Experimental Intervention**

The pudendal nerve block will be done as follow before the spinal anaesthesia:

Ultrasonography allows the visualization of important landmarks: the ischial spine, pudendal artery, sacrospinous ligament, sacrotuberous ligament and pudendal nerve. It also allows real-time needle advancement and confirmation of injectate spread within the interligamentous plane. A low frequency 2-5 MHz curved array ultrasound probe is used. After skin preparation with Povidoneiodine and sterile probe preparation within a transparent plastic sheath, scanning is performed in transverse planes to visualize the ischium forming the lateral border of the sciatic notch. By moving the ultrasound probe in a cephalad-caudal direction, the ischium appears as a progressively lengthening hyperechoic line that is widest at the ischial spine level. The ischium is initially seen as a curved line as it forms the posterior aspect of the acetabulum. When the probe is at the ischial spine level, the ischium will appear as a straight line. At this level, a colour Doppler is used to localize the internal pudendal artery pulsations in close proximity to the ischial spine. Another arterial pulsation is often seen lateral to the tip of the ischial spine and is accompanied by the sciatic nerve. This is the inferior gluteal artery. Mistaking this artery for the pudendal artery will result in sciatic nerve block. The sacrospinous ligament appears as a hyperechoic line in continuity with the ischial spine, with lower echogenicity than bone. Similarly, the sacrotuberous ligament is seen as a light hyperechoic line deep within gluteus maximus muscle and appears parallel and superior to the sacrospinous ligament in ultrasound images. Localization of the pudendal nerve is targeted in the plane between these 2 ligaments. Under ultrasound guidance, a peripheral nerve stimulating needle is inserted from the medial aspect of the probe. It is advanced in line with the ultrasound probe to the medial aspect of the internal pudendal artery. Once the needle passes through the sacrotuberous ligament, a “click” is usually felt and a small volume (1 – 2 mL) of local anaesthetic is injected. The solution appears as a hypoechoic collection, in order to identify the plane between the sacrotuberous and the sacrospinous ligaments and to accentuate the pudendal nerve appearance (pudendal nerve however is not always visible). The needle is inserted medially toward the pudendal artery as the pudendal nerve is principally located medial to this artery. 10 mls of ropivacaine 0.75% are injected within this fascial plane, after negative aspiration. The procedure is then repeated identically on the contralateral side.

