#### **8.2.2 Control Intervention**

The control group will not undergo the pudendal nerve block.

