### **9.2.2 Assessment of secondary outcomes**

Opioids drugs as needed, length of hospital stay and complications data will be registered by the care providers in the postoperative period on specific printed formularies.

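### The nurses who record VAS are declared blind, but there is no sham block and no described step that hides the block from ward staff; those recording opioids are not stated to be blind

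*Combined protocol and SAP*

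**What the plan says.** Section 6.2.2 makes the blinding claim: "The nursing personnel and patients that will fulfil the VAS scale formularies at 6, 12, 24, 48 hours are blinded", and it adds that "they will not know the arm of treatment". Section 6.1 also describes the nurses as blinded. Under section 9.2.1 the VAS, which is the primary outcome, is entered either by nurses on the CRF or by the patient on a separate form.

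The safeguard is stated in section 6.2.1 and repeated in the Synopsis and in sections 6.1 and 7.3: "Only the physician responsible for the study, the anaesthetist and the surgeons will be informed about the treatment arm".

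On the two arms, section 6.1 says "The comparator is no treatment" and section 8.2.2 says "The control group will not undergo the pudendal nerve block". The Synopsis makes clear that controls still have a spinal: "Group B will undergo Milligan-Morgan hemorrhoidectomy under spinal anaesthesia". In Group A, section 8.2.1 describes antiseptic skin preparation, ultrasound scanning and a needle injection, and then states "The procedure is then repeated identically on the contralateral side".

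Section 9.2.2 covers as-needed opioids, length of stay and complications. These "will be registered by the care providers in the postoperative period on specific printed formularies". No section says whether those care providers are the blinded nurses, or whether they are blind at all.

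**The concern.** The section headed as blinding procedures says who is blind but gives no procedure. It does not mention a sham, a matched dressing, a screen or study forms free of arm information. The two arms differ physically at the block sites, and a spinal given to everyone does not conceal that difference from staff who see the skin. This is therefore separate from whether the patient can tell which arm he or she is in.

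A nurse who knows the arm may ask about or record pain differently. Staff who know the arm may differ in how they handle or record as-needed opioids, and opioid use in turn affects VAS. The resulting bias would tend to follow staff expectation. With a control arm that has no sham, staff would probably expect the block to help.

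**Working it through.** **1. Claim against mechanism**

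| Question | What the supplied text gives | Where |
|---|---|---|
| Who is declared blind? | Nurses and patients completing VAS forms | 6.1, 6.2.2 |
| Who may know the arm? | Study physician, anaesthetist, surgeons | Synopsis, 6.1, 6.2.1, 7.3 |
| Is there a sham or matched procedure? | None; Group B has the spinal only | Synopsis, 6.1, 8.1.1, 8.2.2 |
| What differs at the block sites? | Skin preparation and punctures on both sides, Group A only | 8.2.1 |
| What conceals that difference? | Nothing described | – |
| Who enters VAS? | Nurse or patient; proportions not given | 9.2.1 |
| Who enters opioid use? | Care providers, not stated to be blind | 9.2.2 |
| What does the code-break section cover? | Access to the allocation when complications occur, not protection of the blind | 6.3 |

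The disclosure rule says who is told. It does not deal with what can be seen or read. For VAS there is a blinding claim without a described means. For opioids there is no explicit blinding claim, unless the care providers happen to be the nurses of 6.2.2.

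**2. The plan's own figures (section 11.2)**

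- Dropout step: 18 / (1 − 0.10) = 20 per group. This reproduces.
- The 18 per group cannot be reproduced, because neither the control mean nor the SD of VAS is given. Solving backwards for a two-sided 5% t-test with 80% power, 18 per group implies a difference of 0.96 SD. Standardized units are therefore the only usable scale.

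**3. Illustration of size (the shifts are assumptions)**

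Suppose the block has no true effect, but knowledge of the arm moves the recorded group difference by b SD, net over all patients. For one two-sided t-test with n = 20 per arm:

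- degrees of freedom = 2 × 20 − 2 = 38; critical value = 2.024
- non-centrality = b × √(n/2) = b × √10
- error rate = P(T > 2.024) + P(T < −2.024) under the non-central t

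| Assumed net shift b | Non-centrality | Error rate | b as share of 0.96 SD |
|---|---|---|---|
| 0.1 SD | 0.316 | 6.1% | 10% |
| 0.2 SD | 0.632 | 9.5% | 21% |
| 0.3 SD | 0.949 | 15.2% | 31% |

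**4. Dilution by patient-recorded VAS**

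The net shift is roughly the share of readings that nurses record, times the shift in those readings. The share is not documented. If it were one half (assumption), shifts of 0.1, 0.2 and 0.3 SD in the nurse-recorded readings would become net shifts of 0.05, 0.10 and 0.15 SD, with error rates of 5.3%, 6.1% and 7.5%.

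**The case against.** The strongest case against runs as follows.

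- Four places in the protocol restrict who is informed, and none shows a nurse learning the arm. **This stands.** A reader might infer that the design is bound to unblind the nurses, or that the ward chart reveals the block. The documents support neither: no supplied section says where the block is charted or what is handed over to the ward. The gap is that no means of applying the rule is described.
- The CRF and the outpatient protocol, listed in section 17, were not available and may contain masking steps. **This stands.** If they do, 6.2.2 should refer to them.
- No section says the punctures would be noticeable on the ward between 6 and 48 hours. **This stands.** The physical difference between arms is documented; its visibility later is an inference.
- Group B is not free of needle procedures, because it has a spinal. **Correct.** What it lacks is anything at the pudendal sites.
- A reader might take opioid recording as a breach of the nurse blinding. **Section 9.2.2 does not support that.** It names care providers, for whom no blinding is claimed. It also concerns registering opioids and does not say who offers them.
- The assumed shifts have no basis in the documents, and the planned primary test in section 11.3 is a Friedman test, not one t-test. **Both stand.** The percentages show only how error grows with bias and do not estimate this trial's error rate.

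None of this supplies the missing procedure for a bias control on which the primary outcome relies.

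**Conclusion.** The point holds in a limited form. The plan declares the VAS-recording nurses blind, gives controls no sham, and describes nothing beyond a disclosure rule to keep the signs of the block or the allocation from ward staff. For as-needed opioids it states no blinding of the recorders. It is not shown that nurses will in fact learn the arm.

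The size is unknown. Net shifts of 0.1 to 0.3 SD would take a nominal 5% error to about 6% to 15% with 20 per arm. This assumes no true effect, one t-test and a shift averaged over all patients. Because VAS is self-rated and partly self-recorded, nurse knowledge alone may well produce less. The remedy is cheap, so the change is worth making even if the bias is at the low end.

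**What to change.** First reconcile the order of block and spinal. The opening lines of 3.3 and 8.2.1, and section 6.1, put the block before the spinal; the Synopsis and the later text of 3.3 and 8.2.1 put it after. When the matching step is done depends on this.

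Then add to section 6.2.2:

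- In both arms the anaesthesia team, who already know the allocation, apply the same skin preparation and two identical opaque dressings at the block sites. The dressings stay on until the last in-hospital VAS reading.
- The nurses recording VAS and the staff recording as-needed opioids are not told the allocation.
- The study forms that these staff use carry no arm information.
- If the CRF or the outpatient protocol already contains masking steps, cite them.

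Any limit on what the clinical chart shows, and who may use the section 6.3 route, is for the sponsor to settle together with the safety provisions. Section 6.3 as written does not list ward staff, and section 9.2.3 requires block-related adverse events to be assessed during the stay.

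Cost: two dressings per patient, a little theatre time and some protocol wording. It needs no sham injection and no extra staff.
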